7.3.1.5. Muscle Disorders

Muscle disorders will be defined based on:

- MedDRA HLT: Muscle Disorder
- MedDRA PT: Blood Creatine Phosphokinase Increased

Summaries will be presented by high level term (HLT), preferred term and treatment group.

7.3.1.6. Opportunistic Infections

Opportunistic infections will be defined based on the following list of terms, derived from the preferred term (PT) or low level term (LLT) summarized in [Table 5](#). The FDA terms provided are from the Panel on Opportunistic Infections in HIV-Infected Adults and Adolescents.

Summaries will be presented by preferred term and treatment group.

Table 5: List of Terms for Opportunistic Infections

Term	Code	Level	FDA term (if applicable)	If LLT- under which PT
Acinetobacter infection	10051894	PT	Acinetobacter infection	
Aspergillus infection	10074171	PT	Aspergillosis	
Blastomycosis	10005098	PT	Blastomycosis, extrapulmonary	
Burkitt's lymphoma	10006595	PT	Burkitt's lymphoma	
Oesophageal candidiasis	10030154	PT	Candidiasis of esophagus	
Cerebral toxoplasmosis	10057854	PT	Toxoplasmosis of brain	
Cervix carcinoma	10008342	PT	Cervical cancer invasive	
Coccidioidomycosis	10009825	PT	Coccidioidomycosis, disseminated or extrapulmonary	
Cryptococcosis	10011490	PT	Cryptococcosis, extrapulmonary	
Cryptosporidiosis infection	10011502	PT	Cryptosporidiosis infection, chronic intestinal (> 1 month duration)	
Cytomegalovirus chorioretinitis	10048843	PT	Cytomegalovirus disease (other than liver, spleen, or nodes)	
Cytomegalovirus colitis	10048983	PT	Cytomegalovirus disease (other than liver, spleen, or nodes)	

Table 5: List of Terms for Opportunistic Infections (Continued)

Cytomegalovirus duodenitis	10049014	PT	Cytomegalovirus disease (other than liver, spleen, or nodes)	
Cytomegalovirus enteritis	10049074	PT	Cytomegalovirus disease (other than liver, spleen, or nodes)	
Cytomegalovirus enterocolitis	10049015	PT	Cytomegalovirus disease (other than liver, spleen, or nodes)	
Cytomegalovirus gastritis	10049016	PT	Cytomegalovirus disease (other than liver, spleen, or nodes)	
Cytomegalovirus gastroenteritis	10051349	PT	Cytomegalovirus disease (other than liver, spleen, or nodes)	
Cytomegalovirus gastrointestinal infection	10052817	PT	Cytomegalovirus disease (other than liver, spleen, or nodes)	
Cytomegalovirus infection	10011831	PT	Cytomegalovirus disease (other than liver, spleen, or nodes)	
Cytomegalovirus mononucleosis	10011834	PT	Cytomegalovirus disease (other than liver, spleen, or nodes)	
Cytomegalovirus mucocutaneous ulcer	10065036	PT	Cytomegalovirus disease (other than liver, spleen, or nodes)	
Cytomegalovirus myelomeningoradiculitis	10065621	PT	Cytomegalovirus disease (other than liver, spleen, or nodes)	
Cytomegalovirus myocarditis	10056261	PT	Cytomegalovirus disease (other than liver, spleen, or nodes)	
Cytomegalovirus oesophagitis	10049018	PT	Cytomegalovirus disease (other than liver, spleen, or nodes)	
Cytomegalovirus pancreatitis	10049566	PT	Cytomegalovirus disease (other than liver, spleen, or nodes)	
Cytomegalovirus pericarditis	10056721	PT	Cytomegalovirus disease (other than liver, spleen, or nodes)	
Cytomegalovirus syndrome	10056262	PT	Cytomegalovirus disease (other than liver, spleen, or nodes)	
Cytomegalovirus urinary tract infection	10051350	PT	Cytomegalovirus disease (other than liver, spleen, or nodes)	
Cytomegalovirus viraemia	10058854	PT	Cytomegalovirus disease (other than liver, spleen, or nodes)	
Disseminated cytomegaloviral infection	10049075	PT	Cytomegalovirus disease (other than liver, spleen, or nodes)	

Table 5: List of Terms for Opportunistic Infections (Continued)

Encephalitis cytomegalovirus	10014586	PT	Cytomegalovirus disease (other than liver, spleen, or nodes)	
Pneumonia cytomegaloviral	10035676	PT	Cytomegalovirus disease (other than liver, spleen, or nodes)	
Hepatitis B	10019731	PT	Hepatitis B	
Hepatitis C	10019744	PT	Hepatitis C	
Herpes simplex skin chronic ulcers	10058426	LLT	Herpes simplex ulcers chronic (>1mo)	Under "Herpes dermatitis" PT
Herpes simplex	10019948	PT	Herpes simplex bronchitis	
Herpes simplex pneumonia	10065046	PT	Herpes simplex pneumonitis	
Herpes simplex oesophagitis	10074242	PT	Herpes simplex oesophagitis	
Shingles	10040555	LLT	Shingles when 2 distinct episodes or more than 1 dermatome	Under "Herpes zoster" PT
Histoplasmosis	10020141	PT	Histoplasmosis extrapulmonary	
Histoplasmosis disseminated	10020144	PT	Histoplasmosis disseminated	
HIV wasting syndrome	10050309	PT	Wasting secondary to HIV	
Human polyomavirus infection	10057366	PT	Human polyomavirus infection	
Immunoblastic lymphoma	10053574	PT	Lymphoma immunoblastic	
Isosporiasis	10023076	PT	Isosporiasis, chronic intestinal (> 1 month's duration)	
Kaposi's sarcoma	10023284	PT	Kaposi's sarcoma	
Lymphoid interstitial pneumonia	10062997	LLT	Lymphoid interstitial pneumonia	Under "Interstitial lung disease" PT
Listeriosis	10024641	PT	Listeriosis	
Mycobacterial infection	10062207	PT	Mycobacterium infections, other species or unidentified species, disseminated or extrapulmonary (eg, M. haemophilium, M. fortuitum, or M. marinum)	
Mycobacterium avium complex infection	10058806	PT	Mycobacterium avium complex disseminated or extrapulmonary	
Mycobacterium kansasii infection	10028447	PT	M. Kansasii, disseminated or extrapulmonary	
Nocardiosis	10029444	PT	Nocardiosis	

Table 5: List of Terms for Opportunistic Infections (Continued)

Pneumocystis jirovecii infection	10073756	PT	Pneumocystis jirovecii infection	
Pneumonia recurrent	10066727	LLT	Pneumonia recurrent	Under "Pneumonia" PT
Polyomavirus-associated nephropathy	10065381	PT	Polyomavirus (JC virus or BK virus)-associated nephropathy (including progressive multifocal leukoencephalopathy)	
Primary central nervous system lymphoma	10036685	LLT	Lymphoma primary of brain	
Candidiasis of bronchi	10064443	LLT	Candidiasis of bronchi	Under "Respiratory moniliasis" PT
Candidiasis of trachea	10064459	LLT	Candidiasis of trachea	Under "Respiratory moniliasis" PT
Candidiasis of lung	10007155	LLT	Candidiasis of lungs	Under "Respiratory moniliasis" PT
Salmonella sepsis	10058878	PT	Salmonella sepsis	
Salmonella septicemia	10039445	LLT	Salmonella septicemia, recurrent	Under "Salmonella sepsis" PT
Salmonella sepsis recurrent	10066745	LLT	Salmonella sepsis if recurrent	Under "Salmonella sepsis" PT
Active tuberculosis	10071157	LLT	Any active TB	Under "Tuberculosis" PT
Mycobacterium tuberculosis NOS	10028461	LLT	Mycobacterium tuberculosis, any site, latent or active	Under "Tuberculosis" PT

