**APPENDIX I. OPPORTUNISTIC INFECTIONS**

Potential opportunistic infections include, but are not limited to, the following:

- Acinetobacter infection
- Aspergillosis
- Blastomycosis, extrapulmonary
- Burkitt's lymphoma
- Candidiasis of esophagus, bronchi, trachea, or lungs
- Cervical cancer invasive
- Coccidioidomycosis, disseminated or extrapulmonary
- Cryptococcosis, extrapulmonary
- Cryptosporidiosis infection, chronic intestinal (>1 month duration)
- Cytomegalovirus disease (other than liver, spleen, or nodes)
- Hepatitis B and C
- Herpes simplex bronchitis, pneumonitis, or esophagitis
- Herpes simplex ulcers chronic (>1 month)
- Herpes zoster (Shingles) when 2 distinct episodes or more than 1 dermatome
- Histoplasmosis disseminated or extrapulmonary
- Human polyomavirus infection
- Isosporiasis, chronic intestinal (>1 month's duration)
- Kaposi's sarcoma
- Listeriosis
- Lymphoid interstitial pneumonia
- Lymphoma immunoblastic
- Lymphoma primary of brain
- Mycobacterium avium complex or *M. kansasii*, disseminated or extrapulmonary Mycobacterium infections, other species or unidentified species, disseminated or extrapulmonary (eg, *M. haemophilium*, *M. fortuitum*, or *M. marinum*)
- Mycobacterium tuberculosis, any site, latent or active
- Nocardiosis
- Pneumocystis jiroveci infection
- Pneumonia, recurrent

- Polyomavirus (JC virus or BK virus)-associated nephropathy (including progressive multifocal leukoencephalopathy)
- Salmonella sepsis
- Salmonella septicemia, recurrent
- Shingles
- Toxoplasmosis of brain
- Any active tuberculosis
- Wasting secondary to human immunodeficiency virus (HIV)

Source: Modified from the Panel on Opportunistic Infections in HIV-Infected Adults and Adolescents. Guidelines for the prevention and treatment of opportunistic infections in HIV-infected adults and adolescents: recommendations from the Centers for Disease Control and Prevention, the National Institutes of Health, and the HIV Medicine Association of the Infectious Disease Society of America. Available at [http://aidsinfo.nih.gov/contentfiles/lvguidelines/adult\\_oi.pdf](http://aidsinfo.nih.gov/contentfiles/lvguidelines/adult_oi.pdf).

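### SAP Table 5 selects tuberculosis by two low-level terms and zoster by one, so the opportunistic-infection table can miss cases that its own labels cover

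*SAP*

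**What the plan says.** SAP 7.3.1.6 sets the selection rule: "Opportunistic infections will be defined based on the following list of terms, derived from the preferred term (PT) or low level term (LLT"), as set out in Table 5. Each row gives a search term, its code, its level, the matching term from the opportunistic-infections panel (the label) and, for most low-level terms, the preferred term above it. The section then gives the display rule: "Summaries will be presented by preferred term and treatment group".

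The rows at issue are:

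- **Zoster:** one row, *Shingles*, low-level term, shown as belonging to the preferred term *Herpes zoster*. Its label is "Shingles when 2 distinct episodes or more than 1 dermatome".
- **Tuberculosis:** two rows, both low-level terms shown as belonging to the preferred term *Tuberculosis*. *Active tuberculosis* has a label covering every active case. "Mycobacterium tuberculosis NOS" has the label "Mycobacterium tuberculosis, any site, latent or active".

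Protocol Appendix I, to which Protocol 7.1.6 refers investigators for expedited reporting, carries the same tuberculosis concepts, including "Any active tuberculosis". For zoster it has "Herpes zoster (Shingles) when 2 distinct episodes or more than 1 dermatome" and, further down, a separate entry for shingles with no condition.

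**The concern.** A low-level term is narrower than the preferred term above it. If selection runs on the low-level term, two reports of the same disease can be treated differently because they were coded to different low-level terms. For tuberculosis the label describes the disease at any site, latent or active, while the search catches only two particular codings of it. For zoster the search catches one coding and ignores the clinical condition in the label.

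Opportunistic infection is an adverse event of special interest in the SAP and an expedited-reporting event in the protocol. The protocol's summary of infections in the intravenous programme (1.3.2.2) says that none was reported. Where counts are that low, one or two missed cases could turn a table with some events into a table with none.

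**Working it through.** No sample size, power or error-rate figure bears on this point. The check is a literal application of the selection rule to the rows of Table 5.

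**1. Levels.** The table has 52 preferred-term rows and 12 low-level-term rows: 52 + 12 = 64. An event is selected if its preferred term is one of the 52 or its low-level term is one of the 12.

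**2. Where the low-level rows sit.** Of the 12, two belong to a preferred term that is itself a row (*Salmonella sepsis*), one has no parent shown (*Primary central nervous system lymphoma*), and nine belong to a preferred term that is not a row: 2 + 1 + 9 = 12. The zoster row and both tuberculosis rows are among the nine.

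**3. Test codings.**

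| Low-level term of the event | Preferred term | Selected? |
|---|---|---|
| *Shingles* | *Herpes zoster* | Yes |
| Any other | *Herpes zoster* | No |
| *Active tuberculosis* | *Tuberculosis* | Yes |
| *Mycobacterium tuberculosis NOS* | *Tuberculosis* | Yes |
| Any other | *Tuberculosis* | No |
| Any (contrast) | *Salmonella sepsis* | Yes |

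**4. Label against search term.** No tuberculosis search term names latent disease or a body site, although one label covers both. Elsewhere the table is broad: cytomegalovirus has 22 preferred-term rows, many of them site-specific, and *Salmonella sepsis* is listed as a preferred term together with two low-level terms under it.

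**5. Does the display rule widen the search?** Suppose each low-level row were meant to pull in its whole preferred term. Then *Pneumonia recurrent* would bring in every event under *Pneumonia*, and *Lymphoid interstitial pneumonia* every event under *Interstitial lung disease*. That cannot be intended. The low-level rows select narrowly, and the sentence on preferred terms governs how selected events are shown.

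**6. The zoster condition.** The requirement of two episodes or more than one dermatome stands only in the label column, and no step in 7.3.1.6 applies it. A single-dermatome event coded *Shingles* is counted. A multi-dermatome event under *Herpes zoster* with another low-level term is not. The error can go either way.

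**7. Other routes into this table.** For anaphylaxis, SAP 7.3.1.2 adds a summary of investigator-suspected events to the term search. Section 7.3.1.6 has no such addition.

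**The case against.** Several points on the other side stand and limit the finding.

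- **Nothing leaves safety reporting.** SAP 7.3 summarises all adverse events by system organ class and/or preferred term and lists every event. Expedited reporting under Protocol 7.1.6 does not depend on Table 5. Only one special-interest table is exposed.
- **Dictionary content is outside the documents.** Table 5 shows two low-level terms under *Tuberculosis* and one under *Herpes zoster*. Whether there are others, and which latent or site-specific tuberculosis preferred terms exist, must be checked in the MedDRA version used.
- **The zoster half is weaker.** A single-dermatome case does not meet the conditional entry, so leaving it out is not an error against that entry. Appendix I also lists shingles unconditionally, so the reference list is itself inconsistent.
- **Review data are uncertain.** The documents do not show that dermatome and episode details are collected in a form that supports review.

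A reader might go further and infer that the table will undercount, that these are two of the likeliest opportunistic infections in this trial, or that the SAP breaches Appendix I. The documents support none of these. They give no expected rate for either disease, and the net zoster error has no certain direction. Appendix I is an open-ended list of examples for reporting and does not define an analysis; SAP 7.3.1.6 cites the panel source and not Appendix I. The supportable conflict lies inside Table 5, between the search term and the label beside it.

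The argument that the search already runs at preferred-term level fails, as step 5 of the working shows.

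**Conclusion.** The point holds as a minor correction. Read literally, Table 5 omits any event under *Tuberculosis* or *Herpes zoster* whose low-level term is not one of the three listed. For tuberculosis this contradicts the table's own labels. For zoster the row can miss cases and can also count cases that do not meet the stated condition.

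The effect is confined to the opportunistic-infection table. Its size cannot be given from the documents and is zero if no such event occurs. The conclusion assumes that Table 5 is applied at the level stated in each row and that other low-level terms exist under the two preferred terms.

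**What to change.** Before unblinding, amend SAP Table 5 as follows:

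1. Replace the two tuberculosis rows with the preferred term *Tuberculosis*, and the shingles row with the preferred term *Herpes zoster*.
2. Check the MedDRA version used for latent and site-specific tuberculosis preferred terms, and add any that are found.
3. Reconcile the two zoster entries in Protocol Appendix I with the Table 5 row. State whether the episode and dermatome condition applies to the summary. If it does, apply it by blinded review of the case data available.

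The cost is a short table edit, a few extra cases to review and a slightly broader table.

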7.3.2. Adverse Events by Subgroup

Overall adverse event categories will be presented for selected subgroups defined in Section 3.4. The categories of adverse events will include:

- Patients with at least one AE
- Patients with at least one treatment-related AE
- Patients with at least one SAE
- Patients with at least one SAE resulting in death
- Patients with at least one AE leading to discontinuation

Selected summaries will also be presented for adverse events by system organ class (SOC), preferred term and subgroup.

7.4. Deaths

If any patient dies during the study all relevant information will be discussed in the patient's narratives included in CSR. A patient listing of deaths will be provided.

7.5. Clinical Laboratory Tests

Analysis of laboratory tests will be based on on-treatment results, as described in Section 7.1. Measurements collected outside of the defined treatment periods will be excluded. All results will be included in the patient listings.

Summary statistics for laboratory tests will be presented at baseline and at each scheduled visit. Actual values and changes from baseline to each visit will be summarized. Shifts (below, within, and above the normal range) from baseline to each visit will be summarized using patient counts and percentages. Shifts from baseline (Grade 0-4) will be provided for creatine phosphokinase (CPK) at each visit, based on the following grading scale:

- **Grade 0:** <1.25 x ULN
- **Grade 1:** 1.25 to 1.5 x ULN
- **Grade 2:** 1.6 to 3 x ULN
- **Grade 3:** 3.1 to 10 x ULN
- **Grade 4:** >10 x ULN

For CPK values $\geq 3.1 \times \text{ULN}$ (Grade 3-4), investigators will be prompted to collect additional information from the patient related to symptoms associated with the elevation and any potential alternate causes. This supplemental data will be reported in the patient listings.

The incidence of potentially clinically significant laboratory values will be summarized using the criteria specified in Table 6; criteria have been provided for adults and adolescents separately. Summaries of potentially clinically significant laboratory values will include all relevant post-baseline values (including scheduled, unscheduled, and early termination visits). A post-baseline laboratory value will be considered potentially clinically significant only if it satisfies the specified criteria and is more extreme (farther from the limit) than the baseline value. Listings for potentially clinically significant laboratory data will be presented. If any patient has a positive pregnancy test, relevant information will be supplied in data listings.

A scatter plot will be provided for the baseline and maximum on treatment value for CPK.

Table 6: Criteria for Potentially Clinically Significant Laboratory Values

Test	Adults (≥18 years)		Adolescents (12 to <18 Years)	
	Criterion value	Change from baseline	Criterion value	Change from baseline
Serum chemistry				
Alanine aminotransferase	≥3xULN	Increase >0	≥3xULN	Increase >0
Aspartate aminotransferase	≥3xULN	Increase >0	≥3xULN	Increase >0
Alkaline phosphatase	≥3xULN	Increase >0	≥3xULN	Increase >0
Gamma-glutamyl transpeptidase	≥3xULN	Increase >0	≥3xULN	Increase >0
Lactate dehydrogenase	≥3xULN	Increase >0	≥3xULN	Increase >0
Blood urea nitrogen	≥10.71 mmol/L	Increase >0	≥10.71 mmol/L	Increase >0
Creatinine	≥177 µmol/L	Increase >0	≥177 µmol/L	Increase >0
Uric acid: Men	≥625 µmol/L	Increase >0	≥625 µmol/L	Increase >0
Women	≥506 µmol/L	Increase >0	≥506 µmol/L	Increase >0
Bilirubin (total)	≥34.2 µmol/L	Increase >0	≥34.2 µmol/L	Increase >0
Creatine phosphokinase	Grade 3: 3.1 to 10 x ULN Grade 4: >10 x ULN	Increase >0	Grade 3: 3.1 to 10 x ULN Grade 4: >10 x ULN	Increase >0

Table 6: Criteria for Potentially Clinically Significant Laboratory Values (Continued)

Test	Adults (≥18 years)		Adolescents (12 to <18 Years)	
	Criterion value	Change from baseline	Criterion value	Change from baseline
Hematology				
Hematocrit: Men	<0.37 L/L	Decrease >0	<0.30 L/L	Decrease >0
Women	<0.32 L/L	Decrease >0	<0.30 L/L	Decrease >0
Hemoglobin: Men	≤115 g/L	Decrease >0	≤100 g/L	Decrease >0
Women	≤95 g/L	Decrease >0	≤100 g/L	Decrease >0
White blood cell counts	≤3 x 10 ⁹ /L	Decrease >0	≤3 x 10 ⁹ /L	Decrease >0
	≥20 x 10 ⁹ /L	Increase >0	≥20 x 10 ⁹ /L	Increase >0
Eosinophils	≥1.5 x 10 ⁹ /L	Increase >0	≥1.5 x 10 ⁹ /L	Increase >0
Absolute neutrophil counts	≤1 x 10 ⁹ /L	Decrease >0	≤1 x 10 ⁹ /L	Decrease >0
Platelet counts	≤75 x 10 ⁹ /L	Decrease >0	≤75 x 10 ⁹ /L	Decrease >0
	≥700 x 10 ⁹ /L	Increase >0	≥700 x 10 ⁹ /L	Increase >0
Urinalysis				
Blood (HGB)	≥2 unit increase from baseline		≥2 unit increase from baseline	
Glucose	≥2 unit increase from baseline		≥2 unit increase from baseline	
Ketones	≥2 unit increase from baseline		≥2 unit increase from baseline	
Total protein	≥2 unit increase from baseline		≥2 unit increase from baseline	

ULN=upper limit of normal range.

If both the baseline and post-baseline values are beyond the same PCS limit, then the post-baseline value will be considered PCS only if it is more extreme (farther from the limit) than the baseline value. If the baseline value is beyond the low PCS limit and the post-baseline value is beyond the high PCS limit (or vice-versa), then the post-baseline value will be considered PCS.

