**3.16.3.1.2. Other On-Treatment Visits (Visits 4 through 17 [EOT])**

During the double-blind treatment period, patients will return to the study center at week 2 and week 4 and then once every 4 weeks ( $\pm 7$  days) thereafter (relative to baseline/DoR) for administration of study drug and assessments until 4 weeks after the final administration of study drug (week 52 or early withdrawal).

The following procedures/assessments will be performed before administration of study drug at each of these visits, unless otherwise indicated:

- Perform urine pregnancy testing (female patients who are not 2 years postmenopausal or surgically sterile only) (excluding week 2 [visit 4]).
- Perform hematology tests (weeks 2, 4, 8, 12, 16, 32, and 52 or early withdrawal only).
- Perform serum chemistry tests (weeks 16, 32, and 52 or early withdrawal only) (a sample for CPK measurement only, will also be collected on weeks 2, 4, 8, 12, and 20).
- Perform full physical examination (week 52 or early withdrawal only).
- Perform brief physical examination (excluding week 52 or early withdrawal).
- Perform vital signs measurements (includes systolic and diastolic blood pressure, pulse, body temperature, and respiratory rate).
- Measure height and weight (weeks 24 and 52 or early withdrawal only; patients 12 to 21 years of age only).
- Perform ECG (week 24, 36, and 52 or early withdrawal only).
- Perform concomitant medication inquiry.
- Perform adverse event inquiry.
- Complete asthma-specific tests.
  - If patient has withheld inhaled long acting and short-acting bronchodilators for the requisite time period, perform pre-bronchodilator spirometry, including FEV1, FVC, and FEF25%-75% (weeks 2, 4, 8, 12, 16, 32, and 52 or early withdrawal only).
  - Perform post-bronchodilator spirometry, including FEV1 (weeks 16, 32, and 52 or early withdrawal only). If inhaled bronchodilators were used within the specified withhold window, lung function testing should be delayed until the withhold time is met if feasible, or the visit should be rescheduled. If neither option is feasible for the patient, the test may proceed and the deviation recorded.
  - Collect PEF meter (week 52 or early withdrawal only).
  - Collect and review daily asthma control diary, and reinforce diary and PEF compliance (excluding week 2).
  - Complete the ACQ-6 (may be completed after study drug administration during the 1-hour observation period.)

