#### **4.4.1. Discontinuation of Study Treatment**

If premature discontinuation of study treatment occurs for any reason, the patient should continue attending remaining study visits while off study treatment. The patient should not be considered withdrawn from the study due to interruption or discontinuation of study treatment. For this study, it is very important to continue collecting data from all patients whether or not they complete treatment.

If premature discontinuation of study treatment occurs, the patient should return to the clinic as soon as possible for a study treatment discontinuation visit. All evaluations should be performed as an unscheduled visit and include all the assessments specified in the protocol for the early withdrawal visit (see Table 2). The investigator must determine the reason for and the date of discontinuation of study treatment and record this information in both the source documentation and the Study Drug Treatment Completion CRF. The patient's continued participation in the study must be discussed by the investigator and site staff with the patient; the investigator and site staff must also request the patient to continue attending study visits according to the study visit schedule with all assessments completed up to week 52 (visit 17). The CAE event status and safety assessments at week 52 (visit 17) are the priority assessments for patients that prematurely discontinue study treatment. At a minimum, the investigator should make every effort to obtain information regarding serious adverse events, CAE events, and survival status at week 52. A safety follow-up visit (visit 18) should be conducted 12 weeks after visit 17.

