3.2. Safety Analysis Set

The safety analysis set will include all patients who receive at least 1 dose of study drug (including patients from Site [REDACTED]). In this population, treatment will be based upon the treatment patients actually received, regardless of the treatment to which they were randomized. Patients dosed in error, but who otherwise received at least 1 dose of reslizumab, will be assigned to reslizumab for the analysis of safety.

In this analysis, data collected from patients during the treatment period will be included, up to the point at which patients discontinue from their assigned study treatment. For patients who completed treatment in this study, the treatment period will be defined from the first dose of study drug to the end of treatment (week 52) visit. For patients who prematurely discontinue treatment, the treatment period will be defined from the first dose of study drug to the last dose of study drug + 4 weeks. This analysis will be used as the default approach for all safety endpoints.

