4.5. Study Days and Visit Windows

Study days will be numbered relative to the first day of study drug administration. The start of treatment (day 1) is defined as the date on which a patient takes the first dose of study drug, as recorded on the study drug diary. Days will be numbered relative to study start (ie, ..., -2, -1, 1, 2, ...) with day 1 being the start of study drug and day -1 being the day before the start of study drug).

For safety-by-visit summaries, if there are multiple assessments at a post-baseline visit then the last non-missing assessment at that visit will be used for the analysis. This includes assessments at the scheduled and unscheduled visits.

‘Endpoint’ for safety analyses and summaries is the time point when the last observation was obtained during the treatment period. For patients who completed treatment in this study, the treatment period will be defined from the first dose of study drug to the end of treatment (week 52) visit. For patients who prematurely discontinue treatment, the treatment period will be defined from the first dose of study drug to the last dose of study drug + 4 weeks.

For efficacy-by-visit summaries, only the assessments at the scheduled visit will be summarized. The assessments at unscheduled visits will be listed. For the purpose of the efficacy analysis, assessments collected at an early termination visit will be considered as the next scheduled visit for that assessment if at least 3 but no more than 5 weeks elapsed since the date of the last medication intake.

Efficacy-by visit summaries will be presented on-treatment. In this context, ‘endpoint’ will be defined as the last observation obtained at a scheduled or qualified early termination visit during the treatment period. For patients who completed treatment in this study, the treatment period will be defined from the first dose of study drug to the end of treatment (week 52) visit. For patients who prematurely discontinue treatment, the treatment period will be defined from the first dose of study drug to the last dose of study drug + 4 weeks.

For selected variables, additional sensitivity analyses may be presented utilizing all data collected over the entire course of the study including data collected after withdrawal for patients who prematurely discontinue from treatment. In this context, ‘endpoint’ will be defined as the last observation obtained at any post-baseline scheduled or qualified early termination visit.

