7. SAFETY ANALYSIS

7.1. General

The safety analysis set will be used for all safety analyses, unless otherwise noted. Summaries will be presented by treatment group actually received.

In this study, patients are encouraged to remain in the study and complete the remaining study assessments even after withdrawing from treatment. The assessment of safety in this context will be based on measurements and events recorded during the treatment period (on-treatment). On-treatment assessments will be defined as events and measurements occurring between the first dose of study drug and the end of treatment (week 52) visit for patients who complete treatment and between the first dose of study drug and the last dose of study drug + 4 weeks for patients who discontinued treatment early.

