7.2. Study Drug Administration

The exposure to study drug will be characterized by duration of treatment and by the number of patients receiving at least 1, 2, 3, etc. injections. Total patient years will also be summarized. The summaries will be provided by treatment group and overall, and by baseline stratification factors.

Duration of treatment period is defined separately for patients who completed/discontinued treatment.

- Completed: End of treatment (week 52) visit date – first dose date + 1
- Discontinued: Last dose date – first dose date + 29

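### The 28-day safety cut-off for early stoppers makes no allowance for the ±7-day visit window, so an in-window discontinuation visit on days 29 to 42 drops out of the on-treatment safety summaries

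*SAP*

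**What the plan says.** **Safety period.** SAP 7.1 counts safety data "between the first dose of study drug and the last dose of study drug + 4 weeks for patients who discontinued treatment early". SAP 3.2 repeats this for the safety analysis set ("the treatment period will be defined from the first dose of study drug to the last dose of study drug + 4 weeks"), and SAP 4.5 uses the same bound for the safety endpoint. For completers, the period runs to the actual week 52 visit.

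**Exclusion.** SAP 7.5 (laboratory) states: "Measurements collected outside of the defined treatment periods will be excluded". SAP 7.6 (vital signs), 7.7 (ECG) and 7.8 (physical examination) repeat it. Excluded results stay in patient listings.

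**PCS summaries.** SAP 7.5 says these "include all relevant post-baseline values (including scheduled, unscheduled, and early termination visits"; 7.6 says much the same.

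**Visit timing.** In Protocol Table 2, visits from week 4 to week 52 carry a ±7-day window. Protocol 3.16.3.1.2 has patients return every 4 weeks "thereafter (relative to baseline/DoR) for administration of study drug and assessments until 4 weeks after the final administration of study drug".

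**Stopping visit.** Protocol 4.4.1 says "the patient should return to the clinic as soon as possible for a study treatment discontinuation visit", with all early-withdrawal assessments.

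**Efficacy comparison.** SAP 4.5 assigns an early-termination efficacy assessment to the next scheduled visit "if at least 3 but no more than 5 weeks elapsed since the date of the last medication intake".

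**The concern.** Study drug is given only at the clinic, every 4 weeks, and adverse events are asked about before each injection (Protocol 5.1 and 3.16.3.1.2). One realistic way to stop is therefore to attend the next dosing visit, report a problem and decline or be refused the injection. The discontinuation work-up then falls about 28 days after the last dose, right on the cut-off. A visit one day late, and well within its window, moves the whole work-up off-treatment.

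That work-up can matter. After baseline, full chemistry is scheduled only at weeks 16, 32 and 52 or early withdrawal, and ECG only at weeks 24, 36 and 52 or early withdrawal. For a patient who stops before those weeks, the discontinuation visit may be the only full chemistry or ECG after baseline that could count as on-treatment. Adverse events starting after the period have their own post-treatment summary (SAP 7.3); the excluded measurements have none.

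**Working it through.** **1. The cut-off as the SAP counts it.** SAP 7.2 gives treatment duration as "Discontinued: Last dose date – first dose date + 29". An inclusive count to last dose + 28 is (last dose + 28) − first dose + 1 = last dose − first dose + 29. With a last dose 140 days after the first, both give 169 days. So day 28 is the last day included and day 29 the first excluded.

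**2. Possible gap from last dose to next dosing visit.** Both visits vary by ±7 days around dates fixed from randomisation, so the gap is 28 ± 14, or 14 to 42 days. After the first dose (day 0, fixed), the week 4 dosing visit falls on days 21 to 35.

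**3. Share of next-dosing-date visits after day 28.** The documents do not say how visit days scatter, so this is an assumption.
- Both visits independent and uniform over 15 days: 15 × 15 = 225 pairs, of which 15 give exactly 28 days. By symmetry (225 − 15)/2 = 105 exceed 28, and 105/225 = 46.7%.
- Only the next visit varies, as for week 4 after the first dose: 7/15 = 46.7%.
- Symmetric scatter with a share p0 on the exact day: (1 − p0)/2, giving 40% at p0 = 20%, 25% at 50% and 15% at 70%.
- Normal scatter of the gap, rounded to whole days: 31% (SD 1), 40% (SD 2), 43% (SD 3), 45% (SD 4).
- SD 2 with visits on average one day late: 60%; one day early: 23%. Tighter scatter with the same shift goes further (SD 1: 69% or 7%).

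**4. If the visit is held as soon as possible instead.** Spread evenly over days 1 to 35: 7/35 = 20%. All by day 28: 0%.

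**5. What a longer bound would do, under uniform windows.** A 35-day bound still excludes the pairs more than 7 days apart: 7 + 6 + 5 + 4 + 3 + 2 + 1 = 28, and 28/225 = 12.4%. A 42-day bound excludes none.

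**The case against.** The strongest reply is that one dosing interval after the last dose is a coherent bound, used throughout the SAP, and that the protocol does not plan for stoppers to wait until the next dosing date. Protocol 4.4.1 wants the visit as soon as possible. Protocol 3.16.4 wants patients who also leave the study evaluated on their last dosing day or soon after. Visits held that way mostly fall inside 28 days. This stands as a limit on size. It does not remove the gap, because the request runs from the decision to stop, which may itself be made at the next dosing visit.

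Four stronger readings are tempting but not supported:
- *About half of all discontinuation visits are lost.* The 46.7% needs uniform visit days and a stopping visit at the next dosing date. Nor does 7/15 describe the next scheduled visit after the first dose: that is week 1 (US sites) or week 2 ± 3 days, at most day 17, so none would be excluded.
- *The SAP contradicts itself on PCS values.* The word *relevant* in 7.5 and 7.6 may simply mean on-treatment. The text is ambiguous; it neither clearly keeps nor clearly drops these values.
- *Efficacy gets a 5-week period and safety does not.* The 3-to-5-week rule assigns a visit label; SAP 4.5 also ends the efficacy on-treatment period at 4 weeks.
- *The arms are biased.* Nothing in the documents shows a direction or a difference in stopping.

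It also stands that the harm is partly contained. Adverse events are classified by onset date, those causing discontinuation are summarised, and PCS creatine phosphokinase (CPK) elevations are recorded as adverse events and retested (Protocol 7.1.7.2). The outputs most clearly exposed are few: PCS incidence (if the exclusion governs), the plots of maximum on-treatment CPK and weight, and the overall worst-finding ECG shift. The SAP gives no safety rule placing an early-termination visit in by-visit tables, even before day 28.

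**Conclusion.** The gap is real and its effect modest. The safety cut-off for early stoppers equals the nominal dosing interval, so a discontinuation visit that respects its window can still fall on days 29 to 42 and lose its measurements from the on-treatment summaries, while a completer's late week 52 visit never does. SAP 7.5 and 7.6 leave unclear whether the PCS summaries are spared.

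The share of next-dosing-date stopping visits affected is up to roughly half under a uniform window, and about 15% to 60% under the moderate scatters tried. Across all discontinuation visits it is probably lower and could be zero if sites act promptly. The number of patients cannot be given, because the documents state neither the share expected to stop early nor when the stopping visits occur.

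**What to change.** In SAP 3.2, 4.5 (safety endpoint) and 7.1, for laboratory, vital-sign, ECG and physical-examination data in patients who stop early, end the on-treatment period at the later of last dose + 4 weeks and the treatment-discontinuation visit, up to last dose + 6 weeks, in both arms. Six weeks is the 42-day maximum the windows allow. State in 7.5 and 7.6 that the PCS summaries use this same period. SAP 7.7 and 7.8 follow through their reference to 7.1. Adverse-event and exposure periods can stay as they are.

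The cost is a few sentences of SAP text, with no change to data collection or patient management. For some stoppers, up to two more weeks count as on-treatment, and the measurement period then differs slightly from the adverse-event period.
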